PD-L1	programmed cell death-ligand 1
PS	performance status
PT	preferred term
Q2W	every 2 weeks
QTcB	QT interval corrected using Bazett's formula
QTcF	QT interval corrected using Fridericia's formula
SAP	Statistical Analysis Plan

Abbreviations and Special Terms	Definition
TEAE	treatment-emergent adverse event
TNM	tumor, node, metastasis
TURBT	transurethral resection of bladder tumor
ULN	upper limit of normal
ypT0/1/a/isN0M0	pathologic partial responses post therapy
ypT0N0	complete pathologic response post therapy

1. INTRODUCTION

This is an open-label, randomized, umbrella study to investigate the biological rationale and outcomes for selected monotherapy and combination therapies in order to inform of potential neoadjuvant treatment combinations to be further tested in miUBC in participants who are cisplatin-ineligible or those refusing cisplatin therapy and awaiting radical cystectomy.

The purpose of this SAP is to provide details of the statistical analyses that have been outlined in the INCB 24360-901 Protocol.

[REDACTED]

[REDACTED]

The details of the analysis methodology of [REDACTED] pharmacodynamics and results will appear in a separate report.

2. STUDY INFORMATION, OBJECTIVES, AND ENDPOINTS

2.1. Protocol and Case Report Form Version

This SAP is based on INCB 24360-901 Protocol Amendment 4 dated 01 MAR 2022 and CRFs approved 14 DEC 2023. Unless superseded by an amendment, this SAP will be effective for all subsequent Protocol amendments and eCRF versions.

2.2. Study Objectives and Endpoints

[Table 1](#) presents the objectives and endpoints.

Table 1: Objectives and Endpoints

Objectives	Endpoints
Primary	
To determine biologic response in participants with muscle-invasive cisplatin-ineligible or those refusing cisplatin therapy, urothelial carcinoma of the bladder.	For each treatment group, the primary endpoint is the change from baseline in CD8+ lymphocytes within resected tumor.
Secondary	
To evaluate the safety and tolerability of each of the treatment groups.	Safety and tolerability assessed by monitoring the frequency and severity of AEs, including delay in cystectomy due to AEs.
To evaluate the preliminary efficacy of each of the treatment groups.	
• pCR rate, defined as percentage of participants with ypT0N0 in each treatment group.• Major pathological response, defined as residual ypT0/1/a/isN0M0.

Table 1: Objectives and Endpoints (Continued)

Objectives	Endpoints

3. STUDY DESIGN

This is an open-label, randomized, Phase 2, umbrella study of various neoadjuvant therapies for miUBC (ie, [Galsky et al 2011](#)) undergoing radical cystectomy.

This study will test the biological rationale for the use of targeted and immuno-oncology agents for neoadjuvant treatment of cisplatin-ineligible, or participants refusing cisplatin therapy for, miUBC and the potential for subsequent efficacy benefit, as shown with other anti-PD-1 inhibitors, and at doses shown to add minimal/acceptable risk from side effects (ie, positive benefit/risk). The translational endpoints will inform which therapies are viable candidates for further investigation in miUBC. This study is an umbrella design in which future treatment arms may be added or removed at the discretion of the sponsor.

Participants will be randomized into 1 of the following treatment groups:

- Treatment Group A: Epacadostat plus retifanlimab
- Treatment Group B: Retifanlimab monotherapy
- Treatment Group C: Epacadostat monotherapy
- Treatment Group D: Retifanlimab plus INCAGN02385
- Treatment Group E: Retifanlimab plus INCAGN02385 plus INCAGN02390

Tumor tissue will be tested centrally to determine PD-L1 CPS score before enrollment.

[figure not shown]
Participants will be randomized into treatment groups according to the schema in [Figure 1](#). Participants with PD-L1 CPS < 10 or PD-L1 CPS \geq 10 will be randomized at a 2:2:1:2:2 ratio into Groups A, B, C, D, and E, respectively. Participants who pass screening for PD-L1 CPS < 10 will not be randomized into a group once that group has reached the allowed number of participants with PD-L1 CPS < 10. Similarly, participants with PD-L1 CPS \geq 10 will not be randomized into a group once that group has reached the allowed number of participants with PD-L1 CPS \geq 10. This will ensure that the desired proportion of participants who have PD-L1 CPS < 10 and PD-L1 CPS \geq 10 within each group will be enrolled.

For Treatment Group C, the subgroup of participants with PD-L1 CPS < 10 or PD-L1 CPS \geq 10 that reaches 5 participants will hold enrolling participants to that particular subgroup and will continue to enroll until 4 participants in the other subgroup are enrolled.

Screening assessments may be completed over a period of up to 28 days. Treatment cycles are 28 days unless otherwise noted. Each participant enrolled in the study will receive a minimum of 1 treatment cycle if, in the judgment of the investigator, the participant has not met any criteria for study withdrawal. The treatment duration will be approximately 4 to 10 weeks. Radical cystectomy is typically scheduled for approximately 8 to 10 weeks with an average of 8 weeks from the TURBT (ie, approximately Day 56; [Poletajew et al 2014](#)).

Precystectomy assessments will be performed within 2 weeks before surgery. Participants will be followed for safety as well as radiographic imaging for 90 days after cystectomy or the last dose of study treatment in the event cystectomy is not performed.

Figure 1: Study Design Schema

¹ Treatment duration is based on date of radical cystectomy. Participants should receive a minimum of 4 weeks and maximum of 10 weeks of treatment.

The current sample size represents an estimated number of participants per treatment group in order to attain the necessary evaluable paired biopsies. Additional participants will be enrolled in treatment groups to ensure the number of evaluable paired biopsies are obtained. This is a platform design, and additional treatment arms may be added or prematurely stopped for enrollment.

3.1. Randomization

This is an open-label, stratified, randomized study with a translational primary endpoint of change in CD8+ cells within the resected tumor tissue. If eligible for Treatments D and E based on exclusionary criteria, participants will be randomized to Treatment Group A, B, C, D, or E based on PD-L1 CPS values (see Figure 1) at a 2:2:1:2:2 ratio, respectively. If ineligible for Treatments D and E based on exclusionary criteria, participants will be randomized to Treatment Group A, B, or C based on PD-L1 CPS values (see Figure 1) at a 2:2:1 ratio. This will ensure that the planned number of participants will be enrolled into each treatment group with PD-L1 CPS balanced within each treatment group.

3.2. Control of Type I Error

For the primary endpoint, the overall 2-sided Type I error is 0.10.

No adjustment for alpha spending is considered as there are no plans to stop the study early for overwhelming efficacy. A DSMB will be assembled to monitor safety data and study conduct on a regular and ongoing basis during the study. No multiplicity control will be applied to the assessments.

3.4. Schedule of Assessments

Refer to Protocol Amendment 4 dated 01 MAR 2022 for a full description of all study procedures and assessment schedules for this study.

4. DATA HANDLING DEFINITIONS AND CONVENTIONS

4.1. Scheduled Study Evaluations and Study Periods

4.1.1. Day 1

Day 1 is the date that the first dose of any study treatment is administered to the participants.

For randomized participants not treated with any study treatment, Day 1 is defined as the date of randomization.

4.1.2. Study Day

If a visit/reporting date is on or after Day 1, then the study day at the visit/reporting date will be calculated as

$$\text{Day \#} = (\text{visit/reporting date} - \text{Day 1 date} + 1).$$

If the visit/reporting date is before Day 1, then the study day at the visit/reporting date will be calculated as

$$\text{Day \#} = (\text{visit/reporting date} - \text{Day 1 date}).$$

A study day of -1 indicates 1 day before Day 1.

4.1.3. Baseline Value

Baseline is the last nonmissing measurement obtained before the first administration of any study treatment, unless otherwise defined.

For randomized participants not treated with any study treatment, baseline is defined as the last nonmissing assessment before randomization for all parameters.

When scheduled assessments and unscheduled assessments occur on the same day and the time of the assessment or time of first dose is not available, use the following convention to determine baseline:

- If both a scheduled and an unscheduled visit are available on the day of the first dose and the time is missing, use the scheduled assessment as baseline.
- If all scheduled assessments are missing on the day of the first dose and an unscheduled assessment is available, use the unscheduled assessment as baseline.

4.1.4. Handling of Missing and Incomplete Dates

In general, values for missing dates will not be handled unless methods for handling missing dates are specified in this section or relevant sections. The original reported dates collected on the eCRF should be used in all relevant listings. The following rules will be used for handling partial dates for analyses requiring dates.

When calculating the time since diagnosis of cancer, a partial cancer diagnosis date will be handled as follows in the calculation:

- If only the day is missing, then the first day of the month will be used.
- If both the month and day are missing, then 01 JAN of the year will be used.
- If the diagnosis date is completely missing, then the time since diagnosis will not be calculated.

For AEs, an unsolved missing onset date will be imputed by the date of Day 1, which will force the AE to be treatment emergent, with the following exceptions:

- If the stop/resolution date is prior to the Day 1 date, then the AE will be considered as non-treatment emergent.
- If both the month and day are missing, and the last day of the year is prior to the Day 1 date, then the AE will be considered as non-treatment emergent.
- If only the day is missing, and the last day of the month is prior the Day 1 date, then the AE will be considered as non-treatment emergent.

Imputation of start dates for AEs will be handled as follows:

- If only the day is missing, and the first day of the month is after the Day 1 date, then the AE will be considered as treatment emergent, and the incomplete date will be imputed by the first of the month.
- If both the month and day are missing, and the year is after the Day 1 date, then the AE will be considered as treatment emergent, and the incomplete date will be set to 01 JAN.

Imputation of end dates for AEs will be handled as follows:

- If only the day is missing for the AE stop date, the incomplete date will be imputed as the last day of the month.
- If the participant discontinued treatment or died before the last day of that month, the end of treatment or death date should be used for imputation.

When the date of the last dose is used in deriving variables such as duration of treatment or TEAE flag, a missing or partial date of the last dose will be handled as follows:

- If only the day is missing, then the earlier date of the last day of the month or the date that the participant discontinued treatment will be used.
- If both the month and day are missing, then the earlier date of 31 DEC of the year or the date that the participant discontinued treatment will be used.
- Otherwise, the date that the participant discontinued treatment will be used as the date of the last dose.

4.1.5. Cycle Length and Duration

Cycle 1 Day 1 is the day that the first dose of study treatment is administered. The scheduled cycle length is 28 days. The actual Day 1 of subsequent cycles will correspond with the first day of administration of epacadostat, retifanlimab, INCAGN02385, INCAGN02390 in that cycle; thus, treatment cycles may become out of sync with the originally planned schedule, and the cycle length may be different from 28 days. The date of the Day 1 of subsequent cycles recorded on the eCRF will be used as the Day 1 of the subsequent cycles.

Treatment Group A will receive retifanlimab 500 mg (25 mg/mL liquid formulation) IV over 30 (+ 15) minutes on Day 1 of each 28-day cycle and epacadostat 600 or 400 mg BID.

Treatment Group B will receive retifanlimab 500 mg (25 mg/mL liquid formulation) IV over 30 (+ 15) minutes on Day 1 of each 28-day cycle. Treatment Group C will receive epacadostat 600 or 400 mg BID. Treatment Group D will receive retifanlimab 500 mg (25 mg/mL liquid formulation) IV over 30 (+ 15) minutes on Day 1 of each 28-day cycle followed by a 10-minute flush and INCAGN02385 350 mg Q2W IV over 30 (-5/+10) minutes followed by a 10-minute flush. Treatment Group E will receive retifanlimab 500 mg (25 mg/mL liquid formulation) IV over 30 (+ 15) minutes on Day 1 of each 28-day cycle followed by a 10-minute flush, INCAGN02385 350 mg Q2W IV over 30 (-5/+10) minutes followed by a 10-minute flush, and INCAGN02390 400 mg Q2W IV over 30 (-5/+10) minutes followed by a 10-minute flush.

4.2. Variable Definitions

4.2.1. Body Mass Index

Body mass index will be calculated as follows:

$$\text{Body mass index (kg/m}^2\text{)} = [\text{weight (kg)}] / [\text{height (m)}]^2.$$

4.2.2. Prior and Concomitant Medication

Prior medication is defined as any nonstudy medication started before the first dose of study treatment.

Concomitant medication is defined as any nonstudy medication that is started accordingly:

- Before the date of first administration of epacadostat, retifanlimab, INCAGN02385, or INCAGN02390 and is ongoing or ends on/after the date of first study treatment administration.
- On/after the date of first administration of epacadostat, retifanlimab, INCAGN02385, or INCAGN02390 and is ongoing or ends during the course of study.

A prior medication could also be classified as "both prior and concomitant medication" if the start date is prior the first dose of study treatment and the end date is on or after first dose of study treatment. In the listing, it will be indicated whether a medication is only prior, only concomitant, or both prior and concomitant.

For the purposes of analysis, all medications will be considered concomitant medications unless the medications can unequivocally be defined as not concomitant.

5. STATISTICAL METHODOLOGY

5.1. General Methodology

Unless otherwise noted, SAS software (SAS Institute Inc, Cary, NC; v9.4 or later) will be used for the generation of all tables, graphs, and statistical analyses. Descriptive summaries for continuous variables will include but not be limited to the number of observations, mean, standard deviation, median, minimum, and maximum. Descriptive summaries for categorical variables will include the number and percentage of participants in each category.

5.2. Treatment Groups

This a randomized, open-label, umbrella study with 5 treatment groups. Participants will be randomized to receive retifanlimab monotherapy, retifanlimab plus epacadostat, epacadostat monotherapy, retifanlimab plus INCAGN02385, or retifanlimab plus INCAGN02385 plus INCAGN02390. Participant data will be summarized by treatment group.

5.3. Analysis Populations

5.3.1. All-Screened Population

The All-Screened Population will include all participants who signed the informed consent form. The All-Screened Population will be used for summarizing the analysis populations.

5.3.2. Full Analysis Set

The FAS will include all participants who were randomized. Participants will be analyzed according to the treatment to which they were assigned at the time of randomization regardless of the actual study treatment that the participant might take during the study.

The FAS will be used to summarize participant disposition, demographics, baseline characteristics, Protocol deviations, prior and concomitant medications, general medical history, disease history, prior systemic therapy, and prior radiotherapy.

5.3.3. Per-Protocol Population

Not applicable.

5.3.4. Enrolled Population

The Enrolled Population will include all participants who were defined as "Completed" on the Screening Disposition eCRF.

5.3.5. Translational-Evaluable Population

The Translational-Evaluable Population will include all participants enrolled in the study who meet the following criteria:

- Completed a baseline scan and has a minimal residual disease.
- Received at least 4 weeks of neoadjuvant study treatment.
 - Treatment Groups A and C: last dose of epacadostat should be within 2 days prior to day of surgery.
 - Treatment Groups A, B, D, and E: last dose of retifanlimab and/or INCAGN02385 and/or INCAGN02390 should be within the 2 weeks prior to day of surgery.
- Provided evaluable paired biopsies (pretreatment core biopsy and surgical resection biopsy).

The Translational-Evaluable Population will be used for the primary efficacy endpoint analysis.

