6.4. Exposure

For participants in the safety population, exposure to epacadostat, retifanlimab, INCAGN02385, and INCAGN02390 will be summarized descriptively as the following:

- **Number of cycles of epacadostat:** number of cycles with a nonzero dose of epacadostat.
- **Number of cycles of retifanlimab:** number of cycles with a nonzero dose of retifanlimab.
- **Number of cycles of INCAGN02385:** number of cycles with a nonzero dose of INCAGN02385.
- **Number of cycles of INCAGN02390:** number of cycles with a nonzero dose of INCAGN02390.
- **Duration of treatment with epacadostat (days):** date of last dose of epacadostat – date of first dose of epacadostat + 1 – days of interruption.
- **Duration of treatment with retifanlimab (days):** date of last dose of retifanlimab – date of first dose of retifanlimab + 1.
- **Duration of treatment with INCAGN02385 (days):** date of last dose of INCAGN02385 – date of first dose of INCAGN02385 + 1.
- **Duration of treatment with INCAGN02390 (days):** date of last dose of INCAGN02390 – date of first dose of INCAGN02390 + 1.

- **Average daily dose of epacadostat (mg/day):** total actual epacadostat dose taken (mg) / duration of treatment with epacadostat (days).
Total actual dose taken will be calculated based on the information entered in the Drug Accountability Epacadostat eCRF.
- **Average dose of retifanlimab (mg):** total actual retifanlimab dose taken (mg) / number of treatments with retifanlimab.
Total actual dose taken will be calculated based on the information entered in the Dose Retifanlimab eCRF.
- **Average dose of INCAGN02385 (mg):** total actual INCAGN02385 dose taken (mg) / number of treatments with INCAGN02385.
Total actual dose taken will be calculated based on the information entered in the Dose INCAGN02385 eCRF.
- **Average dose of INCAGN02390 (mg):** total actual INCAGN02390 dose taken (mg) / number of treatments with INCAGN02390.
Total actual dose taken will be calculated based on the information entered in the Dose INCAGN02390 eCRF.
- **Epacadostat dose modifications:** number of participants who had epacadostat dose reduction and interruption.
- **Dose delays and dose interruptions:** number of participants with dose delays and dose interruptions.

All exposure data will be listed.

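### The 2-week last-dose window for the primary set is shorter than the 28-day retifanlimab interval, so on-schedule Group A and B participants can be excluded with no analysis to show the effect

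*SAP*

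**What the plan says.** Section 5.3.5 makes the Translational-Evaluable Population the set for the primary endpoint, and Section 7.2.1 uses it. The set "will include all participants enrolled in the study who meet the following criteria". One criterion is at least 4 weeks of neoadjuvant treatment. Listed under it, for Groups A, B, D and E, is that the "last dose of retifanlimab and/or INCAGN02385 and/or INCAGN02390 should be within the 2 weeks prior to day of surgery".

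Section 4.1.5 gives retifanlimab "minutes on Day 1 of each 28-day cycle" in all four groups that receive it. INCAGN02385 (Groups D and E) and INCAGN02390 (Group E) are given every 2 weeks. Groups A and B receive neither. The same section accepts that "treatment cycles may become out of sync with the originally planned schedule".

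On duration, the footnote to the design schema in Section 3 says "Participants should receive a minimum of 4 weeks and maximum of 10 weeks of treatment". On shortfalls, Section 3 says "Additional participants will be enrolled in treatment groups to ensure the number of evaluable paired biopsies are obtained". Section 3.3 plans 16 pairs in each of Groups A and B and states more than 95% power. Section 7.2.3 marks sensitivity and supportive analyses as not applicable, and Section 5.3.3 does the same for a per-protocol population.

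**The concern.** A 14-day look-back cannot cover a drug given every 28 days. For roughly half of each cycle, a Group A or B participant who is exactly on schedule is outside the window. The participant may have a good baseline core, a good resection sample and a permitted treatment duration, and still leave the primary analysis without having departed from the plan.

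Two things are at stake. First, the primary result in Groups A and B would come from pairs selected by where surgery fell relative to the last infusion, and nothing planned would show whether that matters for the CD8 result. Second, the set in Groups D and E is not fixed by the text. With three antibodies joined by *and/or*, two programmers could build different sets from the same data. The word *should* adds some doubt about whether the rule excludes at all, although the lead sentence of Section 5.3.5 points to a binding criterion.

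**Working it through.** **1. The plan's own power figure.** Inputs from Sections 3.2, 3.3 and 7.2.1: paired t-test with n − 1 degrees of freedom, mean change of 1 SD, 2-sided alpha 0.10. Power comes from the noncentral t distribution with noncentrality √n × 1.

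| Pairs | Power |
|---|---|
| 8 | 81.5% (SAP, Group C: 80%) |
| 10 | 89.8% |
| 11 | 92.4% |
| 12 | 94.5% |
| 13 | 96.0% |
| 16 | 98.5% (SAP, Groups A and B: > 95%) |

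Both stated figures are reproduced. The claim of more than 95% holds down to 13 pairs.

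**2. Dates in Groups A and B.** Dosing on Day 1 of each 28-day cycle gives Days 1, 29 and 57. Four to 10 weeks after Day 1 is Day 29 (1 + 28) to Day 71 (1 + 70), which is 43 possible surgery days. The rule is met when surgery day − last dose day ≤ 14.

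| Surgery day | Last dose | Gap (days) | Meets window |
|---|---|---|---|
| 43 | 29 | 14 | yes |
| 44 | 29 | 15 | no |
| 56 | 29 | 27 | no |
| 58 | 57 | 1 | yes |
| 71 | 57 | 14 | yes |

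Days 44 to 56 fail: 13 days, with gaps of 15 to 27 days. On Days 29 and 57 the answer depends on a dose given on the day of surgery. The wording asks for a dose before that day, which disfavours counting it. If it is not counted, the gap is 28 days and these two days fail as well, making 15.

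**3. The 4-week criterion does not already remove these participants.** Section 6.4 defines retifanlimab duration as "date of last dose of retifanlimab – date of first dose of retifanlimab + 1". With doses on Days 1 and 29 this is 29 − 1 + 1 = 29 days, which is over 4 weeks. Someone with surgery on Days 44 to 56 meets that criterion and fails only the window.

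**4. Cycle drift.** Suppose the second dose slips a week, giving Days 1, 36 and 64. Days 29 to 35 fail (7 days) and Days 51 to 63 fail (13 days), so 20 of 43 fail, or 22 if Days 36 and 64 are not counted. The gap moves and does not close.

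**5. Groups D and E.** Doses every 2 weeks fall on Days 1, 15, 29, 43, 57 and 71, so no surgery day is more than 14 days after the last one. If any one antibody suffices, 0 of 43 days fail. If every antibody must comply, retifanlimab fails on the same days as in step 2.

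**6. Illustration of size.** The SAP gives no distribution of surgery day from first dose. Assume on-schedule dosing and surgery equally likely on each of Days 29 to 71.

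- Failing: 13/43 = 30%, or 15/43 = 35%.
- Qualifying out of 16 pairs: 16 × 30/43 = 11.2, or 16 × 28/43 = 10.4.
- Power at 11 and 10 pairs without top-up: 92.4% and 89.8%.

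**The case against.** The strongest reply is that the two sections do different jobs. One says when drug is given. The other says which pairs are informative about a drug effect in tissue. A recency window is a reasonable choice for a biological endpoint, and a window shorter than the dosing interval narrows the set without making it impossible to fill. Section 3 ties treatment duration to the date of cystectomy, Section 3.4 leaves the assessment schedule to the protocol, and Section 10.1 says this definition was updated from the protocol. The protocol, not seen here, may coordinate surgery with dosing. All of that stands, and it limits how much harm can be claimed. It does not tell a reader of the SAP why on-schedule participants fall out, or which reading of *and/or* applies.

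The second reply is top-up enrolment. It can restore the number of pairs, although Section 3 does not say whether a pair must meet the window to count. It cannot undo selection by surgery date. Listings 2.1.5 and 2.3.1 should let exclusions be traced, but they do not show how the CD8 result changes.

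Stronger readings are tempting and are not supported:

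- A reader might infer that typical Group A and B surgery lands in the gap, because Section 3 puts cystectomy at about Day 56, "with an average of 8 weeks from the TURBT". That clock starts at TURBT, not at first dose, and the SAP does not give the time between them.
- A reader might infer a biased comparison between arms. The planned tests are within group, and the direction of any bias is unknown.
- A reader might infer a further dispute over Group B participants with a single dose, because Section 5.3.5 does not say how 4 weeks is counted. On schedule they are excluded either way. By the Section 6.4 formula one dose is 1 day. By calendar time, surgery is at least 28 days after the dose and fails the window.

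**Conclusion.** The point holds as a cheap improvement. As written and naturally read, Section 5.3.5 excludes on-schedule Group A and B participants with evaluable pairs and surgery on Days 44 to 56, and the SAP neither acknowledges this nor plans an analysis that would reveal its effect. For Groups D and E the rule is not determinate. Confidence in the mismatch is high, because it is date arithmetic from two sections of one document.

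Confidence in its size is low. The 30% to 35% figure rests entirely on the even-spread assumption and on-schedule dosing. Even then, power without top-up stays at about 90% to 92%, above the 80% that the SAP accepts for Group C. The main cost is therefore an unexamined selection and an unsettled primary set, rather than a demonstrated loss of power.

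**What to change.** Before CD8 results are reviewed:

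1. Reconcile the Section 5.3.5 window with the Section 4.1.5 schedule, and state whether the window is a binding exclusion.
2. State whether *and/or* means any one antibody or every antibody received.
3. State how the Section 3 top-up counts pairs in relation to the Section 5.3.5 criteria. Which way to count is the sponsor's decision.
4. In Section 7.2.3, replace the not-applicable entry with a supportive analysis: the same paired t-test on log2 fold change, by group, in all participants with evaluable pairs regardless of the last-dose window.

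The cost is a few sentences and one extra efficacy table, with no new samples or procedures. Item 3 affects enrolment only if the sponsor's answer differs from how pairs have been counted so far. The drawback of item 4 is a more variable interval from last dose to resection, so that analysis sits beside the primary result and does not replace it. No change to dosing or to the timing of surgery is proposed.
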